## Department & Unaffiliated Personnel

### Department

**What Department does the PI belong to?**

anxiety-mood-eating and related disorders

**Within the department, what Center or group are you affiliated with, if any?**

anxiety disorders clinic

## Application for Continuation of Research

### Status

#### Current Status of Study:

All research interventions were completed. Only data analysis is ongoing.

### Summary of Experiences to Date

**Please provide a summary of scientific progress of the study and the experience of research participants, to date. This requirement is designed to allow for the investigator and the IRB to reassess the study's risks and benefits in terms of developments in the field, changing practice patterns, and new IRB policies and procedures.**

The study has concluded and is in the data analysis stage. Recruitment is closed and subject follow-ups have been completed. A total of 12 participants were enrolled in the study with 5 participants enrolling in the past year. None of the participants were withdrawn from the study or discontinued. There are no Serious Adverse Events to report.

### Funding

**Have there been any changes in funding status since the prior approval?**

No

**Have the principal investigator and other investigators made all required disclosures of financial interest in the study sponsor/product?**

Yes

### Summary

**Have there been any study findings, recent literature, or untoward events occurring here or at other sites in the past year which might affect the analysis of the safety, risks or benefits of study participation?**

No

**Have there been any serious adverse events (serious and/or unanticipated problems involving risks to subjects or others at this site which occurred in the past year)?**

No

**Have all study staff with a significant role in the design or implementation of the human subject components of this study received required training in human research subject protections?**

Yes

**Is the study covered by a certificate of confidentiality?**

Yes

**Certificate expiration date (mm/dd/yyyy)**

12/13/2023

### Overall Progress

**Approved sample size**

12

**Total number of participants enrolled to date**

12

**Number of participants who have completed the study to date**

12

**Have there been any significant deviations from the anticipated study recruitment, retention or completion estimates?**

No

**Comments / additional information**

**Sample Demographics**

**Select the # of samples applicable**

Fair

**Specify population**

White Participants

**Total number of participants enrolled from this population to date**

8

**Specify population #2**

Asian Participants

**Total number of participants enrolled from this population to date**

3

**Specify population #3**

Other

**Total number of participants enrolled from this population to date**

1

**Specify population #4**

Female

**Total number of participants enrolled from this population to date**

8

**Specify population #5**

Male

**Total number of participants enrolled from this population to date**

4

**Gender, Racial and Ethnic Breakdown**

Gender Breakdown 8 female participants 4 male participants Racial Breakdown 8 White participants 3 Asian Participants 1 participant who identified as other Ethnic Breakdown 1 participant who identified as Hispanic/Latino 11 participants who did not identify as Hispanic/Latino

**Summary of Current Year's Enrollment and Drop-out**

**Number of participants who signed consent in the past year**

5

**Number of participants currently enrolled**

0

**Did the investigator withdraw participants from the study?**

No

**Did participants decide to discontinue study involvement?**

No

## Procedures

**To create the protocol summary form, first indicate if this research will include any of the following procedures**

- ✓ Collection of Biological Specimens
- ✓ Internet-based Data Collection or Transmission
- ✓ Medication Trial
- ✓ MRI
- ✓ Psychiatric Assessment
- ✓ Use of Investigational Drug or Device

## Population

**Indicate which of the following populations will be included in this research**

- ✓ Adults
- ✓ Adults over 50

**Research Support / Funding**

*This section is to describe the funding sources for your protocol.*

If an internal account is to be used, please describe.

The internal account is  RFMH  CU

If the project is using, or planning to use, external funding, provide the details for each external funding source.

**Compass Pathways**

Principal Investigator on grant/contract	[name]
Status of Grant (select one)	is currently funded
Source of Funding (select one)	Industry
Institute / Agency	N/A
Grant Name	Safety and Efficacy of Psilocybin for Body Dysmorphic Disorder
Grant Number	N/A
Sponsor	Compass Pathways
Is this research initiated by the investigator?	Yes
Site description (select one)	Single Site
Business Office (select one)	RFMH
If the grant/contract includes a subcontract, please describe. (To / From, Name of institution(s). Be sure to specify To or From)	N/A

### Lay Summary of Proposed Research

*This section is intended to provide a basic overview of the study including a description of its purpose, study procedures, and subject population. The summary should provide a concise overview of the study for non-scientific and scientific members of the IRB. Please avoid medical or technical terminology. In general, the abstract of a grant does not provide a suitable lay summary.*

Body dysmorphic disorder is a common condition characterized by symptoms of "imagined ugliness" with debilitating distress, checking and avoidance behaviors, and seeking unnecessary cosmetic medical procedures. Serotonin reuptake inhibitor medications and cognitive behavioral therapy helps some patients, but many do not benefit from existing treatments, and no medications are FDA-approved for this indication. Psilocybin is under development as a treatment of several psychiatric disorders, with placebo-controlled trial evidence of safety and prolonged efficacy for major depression when administered as a single dose with intensive support by a therapist on the day of administration. A single case report in body dysmorphic disorder suggests psilocybin might also have efficacy for this disorder.

In this proposed pilot study, up to 12 adults with body dysmorphic disorder that has not responded to at least one adequate trial of a serotonin reuptake inhibitor will be treated openly with a single oral dose of psilocybin. Procedures will follow those previously established in depression studies of psilocybin. Patients will receive intensive preparation and support from two therapists, including 8-9 hours accompanying the patient on the day of medication administration in the Biological Studies Unit. Follow-up visits to monitor safety and clinical outcome will be conducted at day 1, week 1, and months 1, 2, and 3 post-administration. Resting state MRI will be conducted prior to and one day after psilocybin administration to assess the effect of medication on brain circuits.

### Background, Significance, and Rationale

*In this section, provide a brief summary of the status quo of the relevant work field and how the proposed study will advance knowledge. Specifically, identify the gaps in knowledge that your project is intended to fill. If no gaps exist that are obviously and directly related to your project, explain how your proposed research will contribute to the overall understanding of your field. Describe potential impacts of your project within your field of study and in a broader context. Provide a critical evaluation of existing knowledge. The literature review does not have to be exhaustive.*

### Significance and Rationale

Body dysmorphic disorder (BDD) is a debilitating psychiatric disorder in which individuals are preoccupied with perceived defects of their appearance that are not noticeable or appear slight to others, causing significant distress and functional impairment (Phillips 2005). Compulsive checking may occur, and sufferers may seek out unnecessary or risky cosmetic procedures. Most common concerns in BDD involve skin, hair, and nose. BDD has a high prevalence in the general population of 1.7%-2.9% (Buhlman et al., 2010), but it is understudied. To date, there have only been controlled clinical trials to evaluate a single medication class – serotonin reuptake inhibitors (Phillips et al 2002, 2006; Hollander et al 1999) – and a single psychotherapy modality – cognitive-behavioral therapy (Wilhelm et al 2014). Although these treatments can be effective in many, they typically result in only partial symptom improvement and some individuals do not respond to either. There is a need for new intervention approaches.

The rationale for considering psilocybin as a potential treatment for BDD includes a case report (Hanes 2003), in which unsupervised use of psilocybin resulted in symptomatic improvement, as well as evidence for psilocybin efficacy in conditions that frequently co-occur or overlap with BDD, such as obsessive-compulsive disorder (Moreno et al, 2006) and major depressive disorder. The first step in further evaluation of the efficacy and safety of psilocybin for BDD is this proposed open trial, utilizing methods established in prior controlled trials of psilocybin for other disorders.

### **Psilocybin Background** (see Studerus, et al., 2011, for a useful review)

"Magic mushrooms" have been used ceremonially and recreationally for thousands of years. psilocybin produces an altered state of consciousness (ASC) similar to LSD, characterized by marked alterations in perception, mood, and thought, including changes in the experience of time, space, perceptual hypersensitivity, illusions, and pseudohallucinations (i.e. hallucinations with intact reality testing and insight) intensification of affective responses, enhanced ability for introspection, regression to primitive and childlike thinking, and activation of vivid memory traces with pronounced emotional undertones (Fischer, 1971; Geyer and Vollenweider, 2008; Isbell, 1959; Leuner, 1962; Nichols and Chemel, 2006; Rümmele and Gnirss, 1961; Wolbach et al., 1962). These effects are similar to those of LSD, except of shorter duration (4-6 hours instead of 8-12 hours) and psilocybin tended to produce less anxiety, fewer panic reactions and affective disturbances, and milder vegetative side effects than LSD.

Direct pharmacologic effects of psilocybin appear to occur through stimulation (agonism) of various serotonin receptors, including 5-HT2A, 5-HT2B, 5-HT2C and 5-HT1A. The 5-HT2A receptor seems particularly important as many, but not all of psilocybin's effects are blocked by 5-HT2A receptor antagonists. Serotonergic hallucinogens such as psilocybin are considered relatively safe physiologically and do not produce dependence (Johnson et al., 2008; Leuner, 1981; Nichols, 2004).

Studerus et al., 2011, summarized patient experience, physiologic effects and follow-up from 8 studies in which 110 non-psychiatrically ill volunteers were given oral psilocybin 2-28 mg (depending on the study) or placebo and followed for up to 16 months. They report the following dose-dependent symptoms (i.e., the higher the dose, the greater the effect):

- Positive experienced derealization

- 
- Positive experienced depersonalization
  - Changed sense of time
  - Positive mood
  - Mania-like experience
  - Anxious ego dissolution
  - Negative experienced derealization
  - Thought disorder
  - Paranoia
  - Loss of thought control
  - Loss of body control
  - Visionary restructuralization
  - Elementary hall. & illusions
  - Scenery hallucinations
  - Synesthesiae (that is, stimulation of one sensory organ elicits a response from another sensory organ)
  - Changed meaning of percepts
  - Facilitated recollection
  - Facilitated imagination

Psychological Adverse Events included:

- inactivation
- poor concentration
- tiredness
- dazed state
- introversion
- self-confidence (initially increased, later slightly decreased)
- heightened mood
- emotional excitation
- sensitivity
- slight increase in anger
- apprehension-anxiety
- depression
- dreaminess

Most of these adverse events returned to or toward baseline by 24 hours. The main exceptions were what they call "inactivation" and "tiredness" which remained nearly as high at 24 hours as at 3 hours. In addition, though closer to baseline, concentration remained decreased and dazed state and dreaminess were still increased at 24 hours. Griffith, et al. (2016) reports next day headache even with low dose psilocybin (1 mg or 3 mg).

Physical Adverse Events included (in parentheses are % experiencing at highest dose [.315 mg/kg = 22 mg in a 70 kg person (154 pounds)]):

- fatigue (60%)
- exhaustion (22.5%)
- headache, head pressure or facial pain (37.5%)
- lack of energy (22.5%)
- excessive sleep requirement (15%)
- fast exhaustibility (17.5%)
- lack of appetite (17.5%)
- heavy or tired legs (12.5%)
- sleeplessness (5%)
- abdominal pain (7.5%)
- throat pain/irritation (7.5%)
- diarrhea (7.5%)

### Long-term Negative Effects

We found a single case report of persistent psychological effects ("flashbacks") following psilocybin use (Espiard et al., 2005). Griffiths et al. (2016), followed 51 depressed and/or anxious terminal cancer patients for six months after they received 30 mg or 22 mg of psilocybin, reporting "all . . . adverse events resolved fully by the end of the session" except headache which persisted into the next day in two subjects, and "There were no cases of hallucinogen [sic] persisting perception disorder or prolonged psychosis."

While not definitive, given there are hundreds of reported dosings of psilocybin plus unknown numbers of recreational usages, a single case report suggests continuing symptoms long past the drug's active effects are likely rare. Several authors point out that early reports of continuing flashbacks following uncontrolled use of hallucinogens mainly refer to LSD, not psilocybin, and did not address whether other drugs were also used or whether pre-existing psychiatric conditions that will be excluded in the present study were also present. Also, such uses were rarely closely monitored by a facilitator as will occur in the present study.

We are not aware of a study comparing facilitator to no facilitator. Intuitively, it makes sense that having someone present who might assist the individual in making sense of their experience might mitigate against it being as negative an experience as it might otherwise be, and we are not aware of reports of "flash-backs" or other late negative effects in individuals who used psilocybin in the presence of a trained facilitator.

### Addiction Potential

As psilocybin is a Schedule I drug (meant to mean "no currently accepted medical use and a high potential for abuse") it is reasonable to have concern that study participants will become addicted to psilocybin. Our understanding is there is no documented case of an individual becoming addicted to "magic mushrooms" or psilocybin. In fact, individuals who have used either magic mushrooms or psilocybin repeatedly space their use out as if their repeat use is less than several months after a prior use, they achieve only a fraction of the earlier effect. This also argues against there being addiction potential for this compound.

**Specific Aims and Hypotheses**

*Concisely state the objectives of the study and the hypothesis or primary research question(s) being examined. There should be one hypothesis for every major study procedure or intervention. For pilot studies, it is important not to overstate the study's objectives. If there are no study hypotheses, describe broad study goals/aims.*

1. Psilocybin will be acceptable to, and safe and well tolerated by, patients with BDD
2. Symptoms of BDD will improve after psilocybin administration, with persistent improvement over 3 months of follow up
3. Resting state functional connectivity of the default mode network will increase from pre- to post-treatment

**Description of Subject Population**

*In this section, you are to describe each subject population of the study. The demographics of the population should reflect the gender and ethnic distribution of each population being studied. Enter each subject population's sample size, Gender, Racial, and Ethnic breakdown, and finally, describe each subject population.*

**Example:**

**Sample subject population:**

Subject Population	Number of completers required to accomplish	Projected number of subjects who will be enrolled to obtain required	Age range of subject population

## Protocol Summary Form

	study aims	number of completers	
Adults with BDD	12	12	18-55

### Gender, Racial, and Ethnic Breakdown:

#### Gender Breakdown

4 male participants

8 female participants

#### Racial Breakdown

8 White participants

3 Asian participants

1 participant who identified as "Other"

#### Ethnic Breakdown

11 Non-Hispanic/Latinx Participants

1 Hispanic/Latinx participant

#### Description of subject population:

Study sample will consist of adult participants between the ages of 18-55 with a diagnosis of Body Dysmorphic Disorder.

### Suicide Risk Management Plan

*This section will include all information regarding the Suicide Risk Management Plan.*

The study is in data analysis and is not currently enrolling or recruiting participant so this would not be applicable to us.

### Recruitment Procedures

*This section will include all information regarding your study's recruitment process/procedures.*

Describe settings where recruitment will occur. Virtual through websites RecruitMe.com, Craigslist and ClinicalTrials.gov. Recruitment has ended for this study.

## Protocol Summary Form

How and by whom will subjects be approached and/or recruited? Recruitment has closed for this study as of April 2022. When recruitment was open, subjects were recruited through the above websites and were approached by study coordinator, [name].

How will the study be advertised/publicized? Study will be advertised on the above websites, but recruitment has closed as of April 2022.

Attach any ads/recruitment materials requiring review at this time in the Uploads section.

### Clinical Trials:

Please provide the NCT Registration Number for your Clinical Trial. NCT04656301

**YOU MUST REGISTER AT [ClinicalTrials.gov](https://clinicaltrials.gov) IMMEDIATELY UPON RECEIPT OF IRB APPROVAL AND **PRIOR TO ENROLLMENT** OF THE FIRST SUBJECT. YOU WILL BE PROVIDED WITH A NCT REGISTRATION NUMBER ON REGISTRATION. PLEASE REVISE THIS SECTION OF THE PROTOCOL SUMMARY FORM TO INCLUDE THE NCT NUMBER AND RE-SUBMIT AS AN AMENDMENT TO THE IRB.**

### Concurrent Research Studies

*In this section, please identify if subjects in this study participate in or will be recruited from other studies.*

Describe where subjects are recruited from. N/A

Describe the recruitment source for (Must provide IRB Number, PI and Title). N/A

### Inclusion/Exclusion Criteria

*This section details your study sample(s) and addresses the requirement for risk minimization.*

*You may choose to divide your sample by population (healthy controls vs. patient population) or by procedure (subjects who will have an MRI vs. those who will not) and then define different sets of criteria for each.*

*For each sample, create or insert a table to describe detailed criteria for study inclusion and exclusion and the method you will use to ascertain each criterion. The method of ascertainment may describe tests, scales and instruments. When relevant, indicate the level of training of the person who will make the assessment (e.g. clinical interview by a psychiatrist).*

*Inclusion/Exclusion Criteria need to be numbered and listed in outline form (see Table template below).*

#### Adults (18-55) with a Diagnosis of Body Dysmorphic Disorder

CRITERION	METHOD OF ASCERTAINMENT
------------------	--------------------------------

## Protocol Summary Form

Inclusion:	
1. Age 18-55	Date of birth
2. DSM-5- body dysmorphic disorder, non-delusional subtype, for >6 months by history. Non-delusional subtype will be operationalized by Brown Assessment of Beliefs Scale (BABS) 6-item total <18 (Phillips et al., 2006)	SCID -5 BDD module, BABS
3. At least moderate severity of BDD, operationalized by total score >24 on the Yale-Brown Obsessive-Compulsive Scale Modified for Body Dysmorphic Disorder (BDD-YBOCS),	BDD-YBOCS
4. At least moderate overall severity, operationalized by score of at least moderate (4 or greater) on the CGI severity scale	CGI severity scale
5. History of intolerance of, or nonresponse to, a prior adequate trial of an SSRI ( $\geq$ 2 months of fluoxetine 20 mg/day or equivalent), SNRI, or clomipramine	Psychiatric History
6. Currently in psychotherapy (other than CBT for BDD)	Psychiatric History
7. Able to provide informed consent	Psychiatric Assessment
Exclusion:	
1. Current major depressive disorder of greater than moderate severity (17-item Hamilton Rating Scale for Depression total >20)	Hamilton Rating Scale for Depression

2. Current or past DSM-5 bipolar disorder, psychotic disorder, or borderline personality disorder. First degree relative with psychotic disorder or bipolar I disorder.	MINI, family history
3. DSM-5 alcohol or drug use disorder in the past 3 months, or positive result on urine drug screen for illicit substance of abuse (except that prior cannabis use subthreshold for abuse diagnosis will be permitted if discontinued >24 hours prior to dosing)	MINI, urine drug screen
4. Current clinically significant suicidality or a suicide attempt within the past year	Psychiatric Assessment, MINI, CSSR (items 3 or 4 rated “yes” for active suicidal ideation)
5. Need for inpatient or partial hospital treatment	Psychiatric Assessment
6. Mental retardation, dementia, brain damage, or other cognitive impairment that would interfere with participation	Psychiatric Assessment and History
7. Body image concerns accounted for primarily by an eating disorder	Psychiatric Assessment
8. Body dysmorphic disorder criteria not met if weight concerns are excluded	Psychiatric Assessment

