chemistries including thyroid function. A physical examination will be performed at the screening or between screening and Visit 2 (Day -1), with results obtained before psilocybin administration day.

Additional screening will specifically assess eligibility for the MRI portion of the study with the self-rated PhenX Toolkit Hand Dominance Measure and MRI Metal Screening Questionnaire. Contraindications to MRI scanning are:

- Paramagnetic metallic implants or devices
- Contraindicating magnetic resonance imaging or any other non-removable paramagnetic metal in the body (e.g., pacemaker, paramagnetic metallic prosthesis, surgical clips, shrapnel, necessity for constant medicinal patch, some tattoos)
- Being unable to tolerate the scanning procedures (i.e., severe obesity, claustrophobia)

Patients with contraindicated metal or left-handedness will not be offered MRI participation but will complete all other parts of the protocol.

Additional visits (V1a, V1b) will be scheduled as needed to follow up on any lab abnormalities and for patient to establish relationship with study therapist.

Participants will be invited to bring to the screening a companion (friend/family member) whom they would like to support them through the study. Such a companion will be informed of their potential role and will be asked to sign a “caregiver” consent form at the Screening Visit. Caregivers will receive information about the signs of worsening of depression and suicide risk and ways to contact the study team if necessary. The caregiver will complete a questionnaire at screening, Week 3 and Week 12.

**2. Visit 2 (Baseline, Day -1).** Eligibility and willingness to participate will be reassessed. At this visit, the patient meets with the therapist who describes what the experience might be like and how the therapist will handle any difficulties the patient may have with the experience. MRI-eligible subjects will complete acquisition of resting state fMRI. Subjects will also complete an inverted face computer task in which they will view an image of a face and then will be shown an image of two faces (one matching and one non-matching morphed face) and asked to select the matching face as rapidly and accurately as possible. The matching and non-matching faces will be presented either upright or inverted, in various combinations. This task assesses global vs. local visual processing, and it has previously been shown to be abnormal in BDD (Feusner, 2010).

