**3. Visit 3 (Psilocybin Day, Day 0).** The next day, a study psychiatrist again assesses eligibility; those eligible and agreeable receive their dose of psilocybin (25 mg) and spend the next eight hours (longer if needed) with the two therapists; when deemed appropriate, the patient is accompanied home either by a person of their choosing or a staff member. The patient will be reminded that they should not drive or drink alcohol at least until after the end of Visit 4 (next day). Vital signs are taken prior to their dose of psilocybin and prior to leaving the clinic and a study psychiatrist evaluates prior to their departure for whether their condition requires them not to leave. In the latter case, they will either remain in the Biological Studies Unit (BSU) until

cleared by a study psychiatrist or admitted to 5-South inpatient service if they require additional observation overnight.

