### Hospitalization if needed

- Given prior experience with psilocybin treatment, the need for inpatient hospitalization appears unlikely
- In the event that patients require hospitalization they may be admitted to NYSPI 5-South unit.
- Prior to psilocybin dosing [name] will be contacted (email or text [contact]) to ascertain whether backup 5S inpatient bed at NYSPI will be available. In event of lack of availability for such a bed on 5S after it has been offered (e.g., unanticipated issue on inpatient unit) the NYPH. Emergency Room will serve as backup.

**4. Visit 4 (Post-Psilocybin Day 1).** The patient returns to the anxiety clinic and reports any experiences since leaving the clinic as well as having blood, urine, and EKG tests. MRI eligible patients will have another resting state fMRI session, The inverted face task will be repeated.

**5. Visits 5-8 (Post-Psilocybin Weeks 1-3 and 12).** The patient returns 1, 2, 3 and 12 one week later for standard evaluation of psychiatric symptoms, functioning and AE's. These visits may be conducted by phone or secure video.

**6. Telephone visits (Weeks 6 & 9).** The patient is contacted by telephone 6- and 9-weeks post-psilocybin for standard evaluation of psychiatric symptoms and AE's.

**7. Early Withdrawal Visit.** Should the patient or study doctor decide to end the study visits prior to Week 12, if the patient agrees, all Visit 10 (Week 12) ratings including Independent Evaluation will be made.

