## Protocol Summary Form

BDD-REBUS-Q	X		X	X	X	X	X	X	X	X	X	X
Brown Assessment of Beliefs Scale	X		X	X	X	X	X	X	X	X	X	X
Physical Examination	X											
ECG	X				X							
Urinalysis	X		X		X							
Urine for drug/alcohol screening	X		X									
Urine for pregnancy testing*	X		X		X							
Blood for routine laboratory assays	X				X			X				
Vital signs	X		X	X	X							
Height and Weight	X											
PhenX Toolkit Hand Dominance Measure	x											
MRI Metal Screening Questionnaire	x		x		x							
Inclusion & Exclusion Criteria	X		X									
Adverse Events/SAE		X		X	X	X	X	X	X	X	X	X
Resting State fMRI			x		x							
Inverted Face Task			x		x							
Clinical Global Impression - Change					X	X	X	X	X	X	X	X
5Dimension-Altered States of Consciousness				X								
Emotional Breakthrough Inventory					X							
Positive and Negative Affect Schedule			X		X			x	x			
Liebowitz Social Anxiety Scale			x		X				x			X
Psychological Insight Scale					X			X	X			X
Somatomap – 2D Tool			x		x							x
Sheehan Disability Scale			X						x			X
Qualitative Interview				x	x							
Sleep Questionnaire			x		x							
Dysmorphic Concerns Questionnaire			x		x			X	X			x

At any visits in which patient reports clinical worsening, HamD, CSSR, and CGI will be repeated.

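### The cannabis washout is counted from dosing, so it secures only about 0 to 10 hours without cannabis before the single baseline fMRI and face task on Day -1

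*Combined protocol and SAP*

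**What the plan says.** Exclusion 3 (Inclusion/Exclusion Criteria) bars recent substance use disorder and positive urine screens, with one exception: "prior cannabis use subthreshold for abuse diagnosis will be permitted if discontinued >24 hours prior to dosing". The reference point is the dose, on Day 0.

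The imaging schedule is set out under Study Procedures. At Visit 2 (Baseline, Day -1), "MRI-eligible subjects will complete acquisition of resting state fMRI", and the inverted face task is done at the same visit. Visit 3 opens with "The next day, a study psychiatrist again assesses eligibility", followed by dosing. At Visit 4 (Day +1), "MRI eligible patients will have another resting state fMRI session", and the face task is repeated. The Schedule of Study Procedures shows no other scan or face task.

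Hypothesis 3 (Specific Aims and Hypotheses) rests on these two scans: "Resting state functional connectivity of the default mode network will increase from pre- to post-treatment".

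The other provisions that might bear on cannabis are these:
- **Urine screen.** The row "Urine for drug/alcohol screening" is marked at screening and Day -1 only.
- **MRI eligibility.** The listed contraindications are metal and inability to tolerate scanning, and "Patients with contraindicated metal or left-handedness will not be offered MRI participation".
- **Post-dose reminder.** Participants are told that "they should not drive or drink alcohol at least until after the end of Visit 4". Cannabis is not named.

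**The concern.** A washout counted from dosing is a sensible safety rule for the drug. It does not protect a measurement made the day before. A participant can comply fully with exclusion 3 and still have used cannabis within hours of the baseline session.

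Hypothesis 3 is a change score with one scan on each side and no control arm. If recent use shifted a participant's baseline connectivity or face-task performance, that shift would pass straight into the change and could not be told apart from an effect of psilocybin. Repeat scanning and the supported session are also inseparable from the drug in this design, and they are hard to remove. Recent cannabis use can be reduced by rewording one criterion.

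**Working it through.** **Inputs from the documents.** Washout W = 24 h, counted back from dosing (exclusion 3). Baseline session on Day -1 and dosing on the following day (Study Procedures, Visits 2 and 3). Repeat session on Day +1 (Visit 4). Maximum sample 12.

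**Assumed inputs.** The documents give no clock times. I take the dose at 08:00 to 10:00 and the Visit 2 session at 08:00 to 18:00.

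**Step 1: guaranteed cannabis-free time at baseline.** Let gap be the hours from the Visit 2 session to the dose: gap = (24 - session hour) + dose hour. The guarantee is max(0, 24 - gap).

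| Dose (Day 0) | Session (Day -1) | Gap (h) | Guaranteed interval (h) |
|---|---|---|---|
| 08:00 | 18:00 | 14 | 24 - 14 = 10 |
| 09:00 | 17:00 | 16 | 24 - 16 = 8 |
| 09:00 | 12:00 | 21 | 24 - 21 = 3 |
| 09:00 | 09:00 | 24 | 24 - 24 = 0 |
| 10:00 | 08:00 | 26 | 24 - 26 < 0, so 0 |

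The range is 0 to 10 h. It is 0 to 8 h for a 09:00 dose with a session between 09:00 and 17:00. Once the gap reaches 24 h, the rule secures nothing before the session.

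**Step 2: whether another provision fills the interval.**
- The Day -1 urine screen does not, because the exception in exclusion 3 covers a positive result from qualifying cannabis use. A positive screen also does not date that use.
- The MRI criteria do not mention cannabis.
- The eligibility checks at Visits 2 and 3 reapply the same criterion.
- Exclusion 14 lets staff act on safety grounds but sets no interval.
- By contrast, the risk section ties the pregnancy test to each scan, so the protocol does anchor a requirement to the scan elsewhere.

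**Step 3: the same 24 h counted from Visit 2.** The guarantee at baseline becomes more than 24 h at any clock time. In hours before dosing it is 24 + gap: 24 + 14 = 38 to 24 + 26 = 50. The dosing washout is therefore still met. The added abstinence equals the gap, 14 to 26 h.

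**Step 4: what remains.** Sessions at the same clock time on Day -1 and Day +1 are 48 h apart under either rule. With continued abstinence, the intervals would be more than 24 h at baseline and more than 24 + 48 = 72 h at Day +1. The change removes use within hours of baseline. It does not equalise the two scans.

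**Step 5: leverage of one participant.** Each affected person moves the mean change by 1/12 = 8.3% of their own shift, or 1/8 = 12.5% if only 8 were scanned (assumed, since some participants skip MRI). This shows leverage only. The shift itself is unknown, and the SAP names no test for the fMRI data, so no error rate or power can be attached.

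**The case against.** The strongest objection is that no harm is shown. Nothing in the documents says that cannabis alters default mode connectivity or face-task performance over any interval, or that any of the 12 participants used it near Visit 2. This stands. A reader might infer that the Hypothesis 3 result is confounded by cannabis, but the documents do not support that. They show only that the criterion leaves the possibility open.

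Second, the section exists for risk minimization, and counting from dosing is the natural form of a safety rule. That is right, but the rule is also the only visible control on cannabis before the baseline scan.

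Third, the exposed group is narrow. Use disorders in the past 3 months are excluded, and the exception speaks of prior use that has been *discontinued*. Zero hours would also require someone to use cannabis just before an eligibility reassessment. This makes the extreme case less likely, but it does not lengthen the interval that the rule guarantees.

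Fourth, a reader might infer from the driving and alcohol reminder that cannabis was allowed before the Day +1 scan. That goes too far. *Discontinued* can be read as lasting abstinence, and the consent pages, which may carry instructions on substances, were not available for review.

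Finally, the study is complete, fMRI serves the third aim of a pilot, and the 24 h figure is borrowed from the dosing rule without evidence that it is long enough for imaging. All of this stands and keeps the severity low.

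**Conclusion.** The point holds as a low-severity design weakness. Followed exactly, exclusion 3 guarantees only about 0 to 10 h without cannabis before the single baseline session. That range rests on the assumed clock times. The mismatch itself, a washout counted from Day 0 and a measurement on Day -1, is in the text.

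What is affected is the baseline for Hypothesis 3 and for the face task, for which no hypothesis is stated. The BDD-YBOCS efficacy analysis uses neither measurement and is not affected. The number of users and the size and direction of any effect are unknown, and the effect may be zero.

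A reader might also conclude that participants with a positive Day -1 screen should be dropped from the imaging analysis. The documents do not support this: an undated positive result could remove people who stopped well before the scan, from a sample of at most 12.

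**What to change.** **Criterion (in practice, for any successor protocol).** Require cannabis to be stopped more than 24 h before the Visit 2 session instead of before dosing. Add cannabis to the existing driving and alcohol reminder through Visit 4, so that continued abstinence is explicit. Record the time of last use at Visits 2 and 4.

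**Completed data.** Report how many scanned participants had recorded cannabis use shortly before Visit 2. If there were none, or if the records do not date the use, one sentence saying so is enough. Exclude nobody on an undated positive screen alone.

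**Cost.** One phrase in exclusion 3, one word in the reminder, one recorded time at two visits, and one count from existing records. Cannabis users would abstain about 14 to 26 h longer before dosing.
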